	
requires treatment and suitable for oral administration of study drugs. Subjects should meet the following disease activity criteria: an Eastern Cooperative Oncology Group performance status ≤ 2.
 
Subjects should have laboratory values meeting the following criteria:
 
 alanine aminotransferase/aspartate aminotransferase $\leq 3 \times$ the upper limit of normal (ULN); adequate liver function as indicated by a total bilirubin $\leq 1.5 \times$ ULN (subjects with documented Gilbert's syndrome may have bilirubin $> 1.5 \times$ ULN); absolute neutrophil count $> 1000/\mu\text{L}$; platelet count $> 50,000/\mu\text{L}$; creatinine clearance ≥ 50 mL/minute; and hemoglobin > 8 g/dL.

Study Drug and Duration of Treatment:
	
Ibrutinib 420 mg will be dosed orally (PO), once daily (QD) starting on Day -1.
 
Venetoclax will be initiated on Week 1, Day 1 with an initial 5-day dose ramp-up for venetoclax. Venetoclax 400 mg (target dose) will be dosed PO, QD; an option to increase the dose of venetoclax to 600 mg QD will be available at Week 8 or thereafter if there is evidence of incomplete response and/or if the dose of ibrutinib has been decreased to 280 mg/day or 140 mg/day due to toxicity management. The dose of venetoclax should not be increased to 600 mg/day in subjects with significant venetoclax toxicity. The maximum dose allowed for venetoclax is 600 mg/day.
 
Treatment duration of combination treatment will be as follows:
 
 eligible subjects will proceed to stem cell transplantation after reaching complete remission (CR) (combination therapy will be discontinued but subjects will be followed for disease progression) 2 years, will be given to subjects who are ineligible for stem cell transplantation unless treatment is intolerable or the subject develops progressive disease 
For subjects who continue to derive clinical benefit after 2 years of treatment, AbbVie will work with the investigator to consider the potential continuation of therapy, as per local regulations.

Date of Protocol Synopsis:
	
11 November 2020

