2 INTRODUCTION

2.1 Background and Rationale

Why Is This Study Being Conducted

T-cell prolymphocytic leukemia (T-PLL) is a rare and aggressive T-lymphoid malignancy characterized by proliferation of post-thymic prolymphocytes, usually refractory to current treatment strategies or complicated by relapse and associated with short overall survival. Patients with T-PLL typically experience elevated and exponentially rising lymphocyte counts along with splenomegaly, hepatomegaly, lymphadenopathy, and effusions. Responses to alkylating agents, purine analogs, and polychemotherapy are poor, ranging from 20% to 53% in mostly previously untreated patients with short survival durations. There is very scarce clinical data for the overall response rate (ORR) in the relapsed or refractory (R/R) patient population and the ORR is not expected to be greater than 20%. Therefore, in pretreated patients, responses to non-alemtuzumab therapy are estimated to achieve an ORR of 20%.^{1,2,3}

The use of the monoclonal anti-CD52 antibody alemtuzumab has improved response rates of 50% to 75% or even higher (up to 90%) when applied in the first-line setting.^{4,5} Based on data available, benefit (if any) from a combination of alemtuzumab with purine analogs or polychemotherapy compared to alemtuzumab alone is unclear. Thus far, alemtuzumab remains the most effective treatment option in patients with T-PLL; however, despite relatively high response rates (50% to 90%), all patients eventually relapse with a median progression-free survival (PFS) of less than 12 months. Allogeneic stem cell transplantation is considered a treatment goal for eligible patients since long survival durations have been observed.

In 2 recent ex vivo drug screening studies, consistent activities of B-cell lymphoma (BCL)-2 inhibition in T-PLL were observed.^{6,7} Venetoclax is a potent, selective, and orally bioavailable small molecule inhibitor of BCL-2 that binds with > 1,000-fold higher affinity for BCL-2 (inhibition rate constant [Ki] < 0.010 nM) than for B-cell lymphoma – extra large (BCL-X_L; Ki = 48 nM) or myeloid cell leukemia (MCL)-1 (Ki > 444 nM). Venetoclax (also referred to as ABT-199, A-1195425.0, GDC-0199, RO5537382, Venclexta[®], and Venclyxto[®]) is currently being evaluated for the treatment of patients with chronic lymphocytic leukemia (CLL), small lymphocytic lymphoma (SLL), acute myeloid leukemia (AML), multiple myeloma, and non-Hodgkin's lymphoma (NHL).

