Such an event can result from use of the drug as stipulated in the protocol or labeling, as well as from "special situations," such as accidental or intentional overdose, medication error, occupational or accidental exposure, off-label use, drug abuse, drug misuse, or drug withdrawal, all which must be reported whether associated with an AE or not. Any worsening of a pre-existing condition or illness is considered an AE. Worsening in severity of a reported AE should be reported as a new AE. Laboratory abnormalities and changes in vital signs are considered to be AEs only if they result in discontinuation from the study, necessitate therapeutic medical intervention, meets protocol-specific criteria (see Section 6.2 regarding toxicity management), and/or if the investigator considers them to be AEs.

The investigators will monitor each subject for clinical and laboratory evidence of AEs on a routine basis throughout the study. All AEs will be followed to a satisfactory conclusion.

An elective surgery/procedure scheduled to occur during a study will not be considered an AE if the surgery/procedure is being performed for a pre-existing condition and the surgery/procedure has been preplanned prior to study entry. However, if the pre-existing condition deteriorates unexpectedly during the study (e.g., surgery performed earlier than planned), then the deterioration of the condition for which the elective surgery/procedure is being done will be considered an AE.

If an AE, whether associated with study drug or not, meets any of the following criteria, it is to be reported to AbbVie clinical pharmacovigilance or contract research organization (as appropriate) as an SAE within 24 hours of the site being made aware of the SAE (refer to the Operations Manual Section 4.3 for reporting details and contact information):

Death of Subject	An event that results in the death of a subject.
Life-Threatening	An event that, in the opinion of the investigator, would have resulted in immediate fatality if medical intervention had not been taken. This does not include an event that would have been fatal if it had occurred in a more severe form.
Hospitalization or Prolongation of Hospitalization	An event that results in an admission to the hospital for any length of time or prolongs the subject's hospital stay. This does not include an emergency room visit or admission to an outpatient facility.

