 - Updated male contraception recommendation (Section 5.2) to include the following: "Male subjects who are sexually active with a woman of childbearing potential must agree to use **condoms**, even if the male subject has undergone a successful vasectomy, from Study Day 1 through at least 30 days after the last dose of venetoclax and at least 90 days after the last dose of ibrutinib."
- **Rationale:** To add live vaccines to the list prohibited medications and therapy in Section 5.3.

- Updated the list of prohibited medications and therapy to include live vaccinations during study participation and until at least 4 weeks after the last dose of study drug and only after B-cell or absolute lymphocyte count (ALC) recovery.
- **Rationale:** To update the required safety text in the Protocol Section 6.1.
 - Updated the guidance on the "special situations" that may cause an AE.
 - Added additional guidance to define an AE for the following situations: worsening of a pre-existing condition, worsening in severity of a reported AE, or laboratory abnormalities and changes in vital signs.
 - Added definitions for a Serious Adverse Reaction (SAR) and Suspected Unexpected Serious Adverse Reaction (SUSAR).
- **Rationale:** To fix a discrepancy in the timing of recording adverse events (AEs) as stated in the Protocol, Section 6.1 versus the Operations Manual, Appendix I (Section 4.1).
 - Added language in Section 6.1 to clarify that all AEs reported from the time of study drug administration until 30 days after discontinuation of study drug administration will be collected.
- **Rationale:** To remove reporting guidance for AEs associated with the underlying disease under investigation in the Protocol, Section 6.1 because this is no longer valid protocol language.
 - Deleted all language related to the following: disease progression and the underlying disease under investigation including symptoms that the investigator assesses as specific to disease progression should not be reported as an AE unless it results in a serious outcome.
- **Rationale:** To include laboratory monitoring for TLS for any increase in venetoclax dose.
 - Updated Section 6.2 to include TLS laboratory monitoring for the optional increase of venetoclax to 600 mg at Week 8 or thereafter.
- **Rationale:** To clarify and standardize the recommendations for the management of treatment-emergent infections and anti-infective prophylaxis requirements.

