3.0 Introduction

This statistical analysis plan (SAP) describes the full (safety and efficacy) statistical analyses for venetoclax (ABT-199) Protocol M18-803 dated May 02, 2019. It will provide details of statistical methods to be followed for the study. More details in terms of analysis conventions to guide the statistical programming work will be provided in SPP (Statistical Programming Plan).

Unless noted otherwise, all analyses will be performed using SAS[®] version 9.3 or later (SAS Institute Inc., Cary, NC 27513) under the UNIX operating system.

SAP will not be updated in case of future administrative or minor amendments to the protocol unless the changes have any impact on the analysis of the study data.

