7.2 Analysis of Adverse Events

All summaries/analyses involving AEs will include treatment-emergent adverse events (TEAE) only, unless otherwise specified. TEAE are defined as any event with onset after the first dose of study drug and no more than 30 days after the last dose of study drug. Events where the onset date is the same as the study drug start date are assumed to be treatment-emergent, unless the study drug start time and the AE start time are collected and the AE start time is prior to the study drug start time. If an incomplete onset date was collected for an AE, the AE will be assumed to be treatment-emergent unless there is evidence that confirms that the AE was not treatment-emergent (e.g., the AE end date was prior to the date of the first dose of study drug).

For summaries of AEs related (reasonable possibility) to study drug, at each level of summation (overall, SOC, and PT) each subject is counted only once. If a subject has an AE with unknown relationship, then the subject will be counted in the relationship category of "unknown," even if the subject has another occurrence of the same event with a relationship of "no reasonable possibility" present. The only exception is if the subject has another occurrence of the same AE with the relationship of "reasonable possibility." In this case, the subject will be counted under the reasonable possibility category.

Adverse event data will be summarized and presented using primary MedDRA system organ classes (SOCs) and preferred terms (PTs) according to the MedDRA coding dictionary version 21.0 or higher.

The number and percentage of subjects experiencing treatment-emergent adverse events will be summarized for the following adverse event summaries:

- Any treatment-emergent adverse event.
- Any treatment-emergent adverse event with NCI toxicity (CTCAE version 5.0) grade 3, 4, or 5 adverse events.
- Any treatment-emergent adverse event with NCI toxicity (CTCAE version 5.0) grade 3 or 4 adverse event.
- Adverse events broken down by NCI toxicity grade (Severity).
- Any treatment-emergent serious adverse event.
- Any treatment-emergent adverse event leading to discontinuation of venetoclax.
- Any treatment-emergent adverse event leading to venetoclax interruption.
- Any treatment-emergent adverse event leading to venetoclax reduction.
- Any treatment-emergent adverse event that is rated at least possibly related to venetoclax by the investigator (Reasonable Possibility Related)

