- Any treatment-emergent adverse event leading to discontinuation of ibrutinib.
- Any treatment-emergent adverse event leading to ibrutinib interruption.
- Any treatment-emergent adverse event leading to ibrutinib reduction.
- Any treatment-emergent adverse event that is rated at least possibly related to ibrutinib by the investigator (Reasonable Possibility Related)
- Any treatment-emergent adverse event leading to death.

In addition, selected adverse events will be summarized. The list of such events is shown in [Table 2](#).

Table 2. Selected Adverse Events

Risk	Search Criteria
Tumor Lysis Syndrome (TLS)	SMQ – "Tumour lysis syndrome" (Narrow-scope)
Neutropenia	PT terms – "Neutropenia," "Neutrophil count decreased," "Febrile neutropenia," "Agranulocytosis," "Neutropenic infection," and "Neutropenic sepsis"
Serious Infection, Including Opportunistic Infections	SAEs in the SOC of "Infections and Infestations"
Second Primary Malignancy	SMQ – "Malignant tumours" (Narrow) and "Myelodysplastic syndromes" (Narrow)
Lymphopenia	PT terms – "Lymphopenia" and "Lymphocyte count decreased"
Anemia	PT terms – "Anaemia" and "Haemoglobin decreased"
Thrombocytopenia	PT terms – "Thrombocytopenia" and "Platelet count decreased"
Drug Induced Liver Injury (DILI)	SMQ – "Drug related hepatic disorders – comprehensive search"
Medication Error	SMQ – "Medication error" (broad)
Hemorrhage	SMQ – "Haemorrhagic disorders" (narrow)

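### The SAP's second-primary-malignancy search does not exclude T-PLL, so progression of the study disease could be counted there, depending on how it is reported and coded

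*SAP*

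**What the plan says.** **The search.** SAP Section 7.2, Table 2, pairs each selected risk with search criteria. For second primary malignancy the criteria are the narrow versions of two queries, "Malignant tumours" and the one for myelodysplastic syndromes. The table has no exclusion list and no review step.

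**The time window.** The same section states: "TEAE are defined as any event with onset after the first dose of study drug and no more than 30 days after" the last dose.

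**The study disease.** Protocol Section 2.1: "T-cell prolymphocytic leukemia (T-PLL) is a rare and aggressive T-lymphoid malignancy".

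**What counts as an adverse event.** Protocol Section 6.1: "Any worsening of a pre-existing condition or illness is considered an AE". The current text does not set T-PLL or its progression apart from this rule.

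**Versions.** SAP Section 3.0 says that the SAP describes the analyses for "Protocol M18-803 dated May 02, 2019". The current protocol synopsis is dated "11 November 2020". SAP Section 3.0 also says that minor protocol amendments will not trigger an update unless they affect the analysis of the data.

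**The concern.** The row is labelled as second primary malignancy, but the search looks for malignancy. In a trial where every subject already has one, these are the same only if the study disease is taken out, either by a term exclusion or by someone reading the hits. The SAP provides for neither.

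The gap would matter less if progression of T-PLL were kept out of the adverse-event data. The current protocol no longer does that, and the SAP was written before the change.

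Protocol Section 6.2 lists second primary malignancies among the known potential risks of ibrutinib, so a reader will look at this row. The trial has no control arm in which the same misclassification would show up. It is also small, so a few misclassified subjects move the percentage visibly. Protocol Section 7.6 has the interim analysis cover safety as well as efficacy, and there the denominator is 14.

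**Working it through.** The plan gives no figure to reproduce. The check follows the rules in order and then does one piece of arithmetic for scale.

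**Step 1: can T-PLL progression enter the adverse-event data?** Yes. Protocol Section 6.1 makes worsening of a pre-existing illness an adverse event, and T-PLL is pre-existing in every subject. No current section exempts it. The amendment summary (Protocol Appendix H) is used here only to confirm that the absence is deliberate: "Deleted all language related to the following: disease progression and the underlying disease under investigation".

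**Step 2: can it be treatment-emergent?** Yes. The adverse event is the worsening, so its onset is the date of worsening. Protocol Section 5.5 lists progression on study drug as a reason for withdrawal, and such a progression falls between first dose and 30 days after last dose. Not every progression does. Under Protocol Section 4.1 treatment also ends for transplant after CR, at up to 2 years, or for intolerance. Operations Manual Section 3.11 follows subjects who stop without progression, and their later progressions may fall outside the window.

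**Step 3: would the search pick it up?** Not settled. The documents do not list the preferred terms in the query and give no rule for coding T-PLL progression. SAP Section 7.2 says only that MedDRA version 21.0 or higher is used. A term naming the leukaemia would plausibly be caught; a general disease-progression term might not be.

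**Step 4: if picked up, would anything remove it?** Nothing in SAP Table 2 or the text around it does.

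**Step 5: scale.** Let k be the number of subjects whose T-PLL progression is caught and n the number analysed. The false addition to the row is k/n. The values of n come from the sample-size tables (Protocol Table 6, SAP Table 1).

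| n | One subject adds 1/n |
|---|---|
| 37 | 2.7 points |
| 34 | 2.9 points |
| 31 | 3.2 points |
| 14 (interim) | 7.1 points |

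The documents do not give k. For assumed values with n = 37:

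| k (assumed) | k/37 |
|---|---|
| 0 | 0% |
| 5 | 13.5% |
| 10 | 27.0% |
| 20 | 54.1% |

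The value k = 0 is a real possibility: it applies if progression is coded outside the query, or if study-disease terms are removed at the programming stage.

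**The case against.** **Three conditions must all hold.** Investigators must report progression as an adverse event, it must be coded to a term that names the leukaemia, and that term must lie inside the narrow query. The documents establish only that the first is called for. This stands, and it is why the point says that progression could be counted, not that it will be.

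**The label and the programming plan may cover it.** The risk column already says second primary malignancy, and the query can be read as a retrieval tool only. SAP Section 3.0 leaves programming conventions to the Statistical Programming Plan, which is not among the documents and might contain an exclusion. This stands in part: an exclusion there can be neither confirmed nor ruled out. But Section 7.2 gives Table 2 as the search criteria without deferring them, whereas the subgroup sections (5.2 and 6.5) say expressly that detail will follow in the programming plan. What counts as a second primary malignancy is an analysis definition and belongs in the SAP.

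**The stakes are modest.** Second primary malignancy is not among the adverse events of special interest in Protocol Section 6.1, and SAP Section 4.6 calls the study hypothesis generating. A T-PLL term would probably be noticed in preferred-term output before reporting. This stands as to size. It does not justify leaving a rule that, followed literally, can give a wrong count.

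**Stronger readings that the documents do not support.** A reader might infer that the row would mostly measure treatment failure. That needs the number of treatment-emergent progressions and their coding, and neither is given. A reader might also infer that the serious and fatal adverse-event summaries hide progression among toxicity and need split versions. SAP Section 7.2 and Operations Manual Section 4.2 present adverse events by system organ class and preferred term, so where those summaries follow that convention a progression term has its own line.

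**Conclusion.** The point holds as a specification gap in one safety row. SAP Table 2 counts every hit in a malignancy search as a second primary malignancy, and the current protocol lets worsening of the study disease enter the adverse-event data. Treatment-emergent T-PLL progression could therefore appear in a row meant for new malignancies.

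The size is unknown. It is 2.7 points per affected subject at n = 37 and 7.1 at n = 14, with an assumed range of 0% to 54% for 0 to 20 of 37 subjects. Any value above zero assumes that progression is reported as the protocol says, is coded to a term inside the query, and is not excluded in the programming plan.

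The primary endpoint, the sample size, the futility rule and the error rate are not affected. The change should still be made, because the rule as written leaves the reported rate to how each site words a progression.

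**What to change.** - In SAP Table 2, define the second-primary-malignancy row as the result of the two searches minus listed preferred terms for T-PLL and for its progression or infiltration.
- Add that the sponsor's medical staff review the remaining hits and confirm that each is a new malignancy.
- Update the protocol reference in SAP Section 3.0 and align the SAP with the current Protocol Section 6.1, stating how progression of T-PLL is coded and where it is tabulated. The SAP's own update rule supports this, because a change in which events count as adverse events affects the analysis.

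The cost is a short preferred-term list, a sentence on review, and a version alignment. No data collection changes.

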7.3 Analysis of Laboratory Data

Definition of Baseline

The baseline value for laboratory variables will be defined as:

- For subject hospitalized for TLS prophylaxis, the baseline value will be the lab value taken at hospital admission prior to the subject receiving hydration for TLS prophylaxis (the day prior to the first dose of study drug).
- For subject not hospitalized for TLS prophylaxis, the baseline value will be the 0 hour lab draw prior to the first dose of study drug on Day 1.

Laboratory Assessments for TLS

To determine if a subject's laboratory values qualify for TLS, the Howard criteria will be assessed. The Howard definition for laboratory TLS requires ≥ 2 of the metabolic abnormalities specified in [Table 3](#) post-baseline and within 24 hours of each other.

Table 3. Laboratory Criteria for TLS

Element	Value
Uric Acid	> 476 $\mu\text{mol/L}$ (8 mg/dL)
Potassium	> 6.0 mmol/L (6 mEq/L)
Inorganic Phosphorus	> 1.5 mmol/L (4.5 mg/dL)
Calcium	< 1.75 mmol/L (7 mg/dL)

The following summaries of laboratory criteria will be provided:

- Number and percentage of subjects meeting the definition of laboratory TLS (at least two values meeting the criteria in [Table 4](#), occurring within 24 hours of each other).
- Listing of all values for these four analytes for each subject meeting the definition of laboratory TLS at least once during treatment.

Assessment of Drug-Induced Liver Injury

The number and percentage of subjects in each treatment group who have at least one observed post-baseline value meeting the following criteria will be tabulated: ALT > $3 \times \text{ULN}$, AST > $3 \times \text{ULN}$, AST or ALT > $3 \times \text{ULN}$, total bilirubin value > $2 \times \text{ULN}$, ALT or AST > $3 \times \text{ULN}$ and total bilirubin > $2 \times \text{ULN}$ within 24 hours. A listing of all observed ALT, AST, and total bilirubin values will be generated for subjects with an observed value meeting any of these criteria.

Analysis of Shift from Baseline in Clinical Laboratory Data

For shifts relative to National Cancer Institute Common Toxicity Criteria for Adverse Events (NCI CTCAE version 5.0), baseline and post-baseline laboratory observations (maximum and final) will be categorized as grade 0, grade 1, grade 2, grade 3, or grade 4 according to NCI CTCAE grade version 5.0. For laboratory tests for which a normal range limit is one end of the grade 1 range then values that are either within the normal range or outside it in opposite direction will be classified as grade 0 values.

The baseline and final grades will be defined respectively as the grade of the last measurement collected prior to the first dose of study drug unless specified differently, and as the last post-baseline measurement collected no more than 30 days after the last dose of study drug. The maximum NCI toxicity grade value is the value with highest NCI toxicity grade collected after the first dose of study drug and within 30 days following the last dose of study drug. In cases where multiple values are collected on the same day, the maximum grade value will be selected as the value for that day.

For each variable, shift tables will be generated that cross tabulate the number of subjects with baseline values of grade 0, grade 1, grade 2, grade 3, or grade 4 versus maximum or final observations of grade 0, grade 1, grade 2, grade 3, or grade 4.

Detailed listings of data for subjects experiencing NCI CTCAE grade 3 to 4 blood chemistry and hematology values will be provided. All measurements collected, regardless of the number of days after the last dose of study drug, will be included in these listings.

